3		Unknown [†]	Nasal High Frequency Oscillatory Versus Nasal Intermittent Positive Pressure Ventilation in Neonate After Extubation	
 • Respiratory Insufficiency 	
 • Device: NIPPV • Device: NHFOV 	

[†] Study has passed its completion date and status has not been verified in more than two years.

Activate Windows [^ TO TOP](#)
Go to Settings to activate Windows.

[figure not shown]
[For Patients and Families](#) | [For Researchers](#) | [For Study Record Managers](#)

7. Objective(s) of the study

Primary objective: To assess the pCO₂ after 2 hours of nHFO compared with 2 hours of nSIPPV in crossover study.

Secondary objective: To assess the reintubation rate within 7 days between non-invasive ventilations (nHFO vs nSIPPV) from the latter NIV mode in parallel study

8. Study flow diagram and/or Conceptual framework

9. Literature review

Mechanical ventilation was introduced to treat respiratory failure in preterm infants or sick neonates then improvements in survival.^{1,2} However, the complications from short or long term use of ventilation can result in unintended harm or burden (e.g., air leak syndrome, pneumonia, bronchopulmonary dysplasia, neurological injury, retinopathy of prematurity).^{3,4} To reduce these risks, clinicians should aggressive extubated neonates as early as possible. Respiratory (focus on blood gas as well as partial pressure CO₂ [pCO₂]) or extubation (focus on clinical condition as well as reintubation) failure was worrisome in pediatrician and parents if the neonate was reintubated owing to complete recovery of lung disease or inadequate respiratory drive.

[figure not shown]
[figure not shown]
[figure not shown]
Non-invasive ventilation (NIV) was supported for primary respiratory support (initial mode before endotracheal intubation) or post-extubation. Nasal continuous positive airway pressure (nCPAP) was familiar to NIV mode in neonatal respiratory support. Nowadays, the new NIV modalities are nasal intermittent synchronized positive pressure ventilation (nSIPPV) and nasal high frequency oscillation (nHFO).

[figure not shown]
[figure not shown]
[figure not shown]

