10.7. Participant withdrawal criteria

1. Parents' decision not to participate
2. Reintubation during 4-hour cross-over study

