10.10. Study procedure(s)/stage(s)

[figure not shown]
This study was blocked and stratified randomization. Subjects were equally (1:1) randomized to one of the two treatment sequences (nHFOV–nSIPPV, nSIPPV–nHFOV). The allocation sequence was computer generated by box of four. The allocation concealment was ensured by using identical, opaque, sealed envelopes. An envelope was drawn by a dedicated nurse immediately after enrolment of the infant. The participants were stratified by gestational age and oxygen index (OI = mean airway pressure [MAP]*FiO₂*100/PaO₂). The participants were on the non-blinded and randomized NIV mode for 2 hours and blood gas was analyzed then switched to another NIV mode for 2 hours (cross-over) and blood gas was analyzed repeatedly. There was not a washout period between 2 NIV modes then the last NIV mode was on until no need NIV. We will register in ClinicalTrials.gov before start and enrollment of the participants.

Extubation criteria: The ventilated neonate had a targeted oxygen saturation (SpO₂ > 90%) during on FiO₂ < 0.4 and acceptable blood gas (pH > 7.25, PaCO₂ < 60) with the respiratory setting of

[figure not shown]
1. HFO: flow 6-10 L/min, frequency 10 Hz, MAP = “6-7 (preterm), 7-9 (term)” cmH₂O, dP = 12-20, I:E = 1:1
2. AC: flow 6-10 L/min, rate 30/minute, PIP 12-15 cmH₂O, PEEP = 3 cmH₂O

Intervention nHFOV and nSIPPV were generated by neonatal ventilators (SLE6000 infant ventilators, United Kingdom) using bi-nasal prongs (RAM cannula, NEOTECH[®], USA) or the nasal mask of the same type for both ventilation modes. The size of the prongs was determined by the infant's weight. The largest possible prongs were used, with a snug fit to avoid leakage. Pacifier for preterm and term neonate (JollypopTM, USA) was taken to avoid leakage from the mouth. The disposable ventilator circuit (Fisher & Paykel RT268TM, Evaqua Dual Limb Infant Breathing Circuit Kit with Evaqua 2 Technology and Pressure Line, Flow > 4L/min, New Zealand) was used. The initial NIV setting was⁷

1. nHFO: flow 8-10 L/minute, frequency 10 Hz, MAP = "MAP (before extubation) + 2" or "8 (preterm), 10 (term)" cmH₂O, dP = "2-3 times of MAP with visible chest oscillations" or 25-35 cmH₂O, I:E = 1:1, FiO₂ = "FiO₂ (before extubation) + 0.1-0.2" keep targeted SpO₂ 90-94%

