2. nSIPPV: flow 8-10 L/minute, rate 60/minute, PIP = "PIP (before extubation) + 2-5" or "20 (preterm), 25 (term)" cmH₂O, PEEP = 5 cmH₂O, IT = 0.5 s, FiO₂ = "FiO₂ (before extubation) + 0.1-0.2" keep targeted SpO₂ 90-94%. The highest trigger sensitivity avoiding auto triggering was selected.

The monitoring after extubation was vital signs, clinical manifestations, respiratory distress, and umbilical arterial blood gas. The first blood gas before extubation was routine obtained. After randomization, the initial NIV was started then blood gas was obtained after 2 hours. The participant was switched to another NIV and blood gas was obtained after 2 hours. The participant was continued with the last NIV mode until the NIV was stopped. The participant was excluded if severe respiratory failure with reintubation during 4 hours after intervention. The parameters were adjusted or titrated according to patient tolerance and disappeared respiratory distress, the intervention went on until 4 hours. The NIV was stopped to "room air, oxygen box, low or high flow cannula" when

1. nHFO: MAP = 5-6 cmH₂O, dP = 10-15
2. nSIPPV: PIP/PEEP = 10-12/3-5 cmH₂O

Criteria for extubation failure or reintubation were as follows:

1. Cardiorespiratory arrest or any type of pulmonary hemorrhage
2. Persistent low blood pressure without response to volume expander and vasoactive agents
3. Stupor or persistent drowsiness after initial correction and care
4. Severe respiratory distress
5. Two hours of respiratory acidosis with PaCO₂ > 70 mmHg and pH < 7.2
6. Two hours of hypoxia with PO₂ < 50 mmHg with FiO₂ > 0.6, and maximal pressures given (MAP 20 and PIP 25 cmH₂O in the nHFOV and nSIPPV group, respectively)
7. Apnea occurring three or more times per hour and a heart rate less than 100/min or apnea with required bag-and-mask ventilation.
8. Severe post extubation stridor

In case of extubation failure, the study period was ended prematurely for the respective infant, pCO₂ was measured by blood gas analysis and a mode of ventilation was chosen as

deemed appropriate by the attending staff. In general, infants were treated with intravenous aminophylline then oral caffeine base and were supported before and after the study.

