10.14. Statistical analysis

Descriptive part: Mean (SD), Median \pm IQR

Analytic part: Continuous outcome

1. Carry-over effect = Independent t-test comparing intraindividual sums of measurements from both periods.
2. Treatment effect = Independent t-test comparing intraindividual differences of measurements of nHFOV versus nSIPPV from both periods.
3. Dependent t-test

Regression analysis

Category (reintubation): logistic regression

Time to event (reintubation): Cox's proportion model

Intention-to-treat analysis was applied in case of treatment failure.

$p < .05$ was considered significant

Subgroup analysis was performed

11. Ethical consideration

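### Randomisation is stratified by gestational age and oxygen index, but section 10.14 lists the reintubation models without stratum terms; leaving prognostic strata out keeps the test valid but mildly conservative, at a cost of about 0 to 3 points of power.

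*Combined protocol and SAP*

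**What the plan says.** Section 10.10 describes 1:1 allocation to two treatment sequences. On the method it says "The allocation sequence was computer generated by box of four" and "The participants were stratified by gestational age and oxygen index". It gives no cut-points for either factor and no number of strata.

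The secondary objective in section 7 is "To assess the reintubation rate within 7 days between non-invasive ventilations (nHFO vs nSIPPV) from the latter NIV mode in parallel study". Section 10.10 adds "The participant was continued with the last NIV mode until the NIV was stopped", so the randomised sequence fixes the arm for the 7-day comparison.

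For that endpoint section 10.14 lists "Category (reintubation): logistic regression" and "Time to event (reintubation): Cox's proportion model". It names no terms for either model. It also mentions subgroup analysis, without detail.

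Two further passages affect who is analysed. Section 10.7 lists "Reintubation during 4-hour cross-over study" as a reason for withdrawal, and section 10.10 says "The participant was excluded if severe respiratory failure with reintubation during 4 hours after intervention".

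**The concern.** Permuted blocks of four within strata keep the two sequences within two infants of each other in every stratum. Differences in risk between strata therefore contribute almost nothing to the true sampling variation of the treatment comparison. A model without stratum terms does not know this, and its standard error still includes the between-stratum variation. If the strata are prognostic, that standard error is too large, the test rejects less often than 5% under the null, and some power is lost.

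Two things are at stake, both small. One is efficiency on the secondary endpoint. The other is pre-specification: in a non-blinded trial whose model terms are not written down, adjusted and unadjusted results could both be produced and one preferred once the data are seen.

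**Working it through.** **1. The plan's own figure.** Section 10.9 gives reintubation risks of 0.10 and 0.17 and 373 per arm (401 with continuity correction). With a two-sided alpha of 0.05 and 80% power, the pooled risk is 0.135 and

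n = [1.960 × √(2 × 0.135 × 0.865) + 0.8416 × √(0.10 × 0.90 + 0.17 × 0.83)]² / 0.07² = (0.9472 + 0.4046)² / 0.0049 = 372.9, so 373.

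The continuity correction gives 401.0. Both figures reproduce. The formula has no stratum terms. Its power is 80.0% at 373 per arm and 7.1% at 12 per group, the other size printed in 10.9.

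**2. Assumed gradients.** The documents give no prognostic strength, so it has to be assumed: four equal strata, mean 7-day risks of 17% and 10%, and a common treatment odds ratio across strata. The top-to-bottom odds ratio (OR) is varied. Rounded control risks by stratum are:
- OR 3: 10, 14, 19, 25%
- OR 8: 6, 11, 19, 32%
- OR 18: 3, 8, 19, 38%

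**3. Expected conservatism, by hand.** Under a null risk of 17% the total binary variance is 0.17 × 0.83 = 0.1411. The between-stratum share is the mean squared deviation of the stratum risks from 0.17, divided by 0.1411. The unadjusted standard error is too large by 1/√(1 − share), and the expected type I error is 2 × [1 − Φ(1.96 × that factor)].
- OR 3: (0.07² + 0.03² + 0.02² + 0.08²)/4 = 0.00315; share 2.2%; factor 1.011; type I error 4.7%.
- OR 8: (0.11² + 0.06² + 0.02² + 0.15²)/4 = 0.00965; share 6.8%; factor 1.036; type I error 4.2%.
- OR 18: (0.14² + 0.09² + 0.02² + 0.21²)/4 = 0.01805; share 12.8%; factor 1.071; type I error 3.6%.

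**4. Simulation.** Settings: 746 infants, blocks of four within strata, all infants kept, two-sided 5% Wald tests, 60,000 trials per scenario for the logistic power gap.

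| Top-to-bottom OR | Logistic power gained by adding strata (points) | Unadjusted type I error |
|---|---|---|
| 1 | 0.1 | about 5% |
| 2 | 0.3 | not tabulated |
| 3 | 0.7 | 4.6-4.8% |
| 8 | 1.8 | 4.1-4.4% |
| 18 | 2.8 | 3.5-4.0% |

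The type I errors agree with step 3. At OR 3 and 8 the adjusted test is at 4.9-5.0%. Power levels from 20,000 trials, without and with strata, are 79.8 and 79.9% (no gradient), 80.4 and 81.0% (OR 3), 80.9 and 82.6% (OR 8), and 81.2 and 84.0% (OR 18).

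The mechanism is visible at OR 8: the unadjusted log odds ratio has a true SD of 0.216 but a mean model SE of 0.223, a ratio of 1.032.

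**5. Cox model.** In the same setting, power without and with stratification is 80.3 and 80.8%, 80.8 and 82.5%, and 81.2 and 83.8% at OR 3, 8 and 18. A log-rank version with a separate hazard ratio for each factor (3,000 trials) gives gains from 0.7 points (2 for gestational age, 1.5 for oxygen index) to 3.5 points (4 for each).

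**The case against.** Much of the other side stands.

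- **Silence is not a decision.** Section 10.14 lists model families only, without even the treatment term. A reader might infer that the team has chosen unadjusted models. The documents do not say so, and a regression model admits covariates.
- **Nothing planned is lost.** The 373 per arm comes from an unadjusted formula, and the unadjusted test delivers about 80% with all infants kept. Adjustment adds power above the plan.
- **The size is assumed.** With weak strata the loss is nil or a few tenths of a point. The 3-point end needs stratum risks running from 3% to 38%. The extubation criteria in 10.10 (FiO₂ below 0.4, modest pressures) may also narrow the oxygen index, although when it is measured is not stated and gestational age could still matter.
- **Sample size.** Section 10.9 prints both 12 and 373 per group. At 12, about 12 × (0.10 + 0.17) = 3.2 events are expected, and stratum terms could not be fitted reliably. Section 12 also warns of a recruitment shortfall.

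Two stronger readings are tempting. One is that ignoring the strata invalidates the test. The error runs the other way, since type I error falls below 5%.

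The other is that 5 points or more are at stake because infants reintubated within 4 hours drop out. Gaps of 4.6 to 5.9 points can be produced, but only by combining OR 18, about 15% of the 7-day hazard before hour 4 and a mode difference from hour 0; the 5.9 also needs unequal strata. The documents support none of these. If the modes do not differ before hour 4, the gaps are 0.7, 1.8 and 3.0 points at OR 3, 8 and 18. Under that 15% assumption the exclusion lowers power to about 72-77% with or without strata, which is a separate matter.

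What survives is that the design uses the strata, the analysis text does not mention them, and settling this costs almost nothing.

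**Conclusion.** The point holds as a minor one on efficiency and pre-specification for a secondary endpoint. If the strata predict reintubation and are omitted, the logistic test remains valid and mildly conservative. The loss is about 0 to 1 point of power for gradients up to OR 3, about 2 points at 8, and about 3 points only at 18.

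These sizes rest on four equal strata, 373 per arm, all infants kept, and gradients that the documents do not supply. They do not show a validity failure or a shortfall against the planned 80%, and they do not favour the logistic model over the Cox model or the reverse. At 12 per group the point is immaterial; which size governs enrolment is a separate question.

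**What to change.** In 10.10, state the gestational-age and oxygen-index categories used at randomisation; without them the model terms cannot be defined.

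In 10.14, make the main reintubation analyses:
1. a logistic model with randomised sequence plus those categories;
2. a Cox model stratified by the same categories.

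With about 101 events expected (373 × 0.27), or about 83 under the assumed early exclusions, some strata could be sparse. State in advance that main-effect terms or collapsed categories will then be used. Show unadjusted estimates alongside. If a marginal effect is wanted, report the risk difference standardised from the adjusted logistic model.

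The cost is a few sentences and no new data, because both factors must be known in order to randomise. The small downside is that the adjusted odds and hazard ratios are conditional on the strata, and the plan should say so. The log-scale interval for the odds ratio is also slightly wider. At OR 8 the adjusted log odds ratio is −0.66 (SE 0.230) against −0.62 (SE 0.223) unadjusted, with true odds ratios of 0.52 conditional and 0.54 marginal. The test still gains, because 0.66/0.230 = 2.87 exceeds 0.62/0.223 = 2.78.

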10.12. Data collection methodology

Participant's data and blood gas's result will be recorded in record form.

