11.1. Possible risks/effects in the study, including preventive and alleviation measures

Both interventions, the participants were obtained the blood samples before and after intervention via arterial line to minimize pain from phlebotomy.

The volume of blood sample was 0.4 mL including before and after tests. The maximum allowable blood draw volumes were shown in **Figure 6**.

Maximum allowable blood draw volumes:

PATIENT'S WEIGHT		TOTAL VOLUME	MAXIMUM mL IN ONE BLOOD DRAW	MAXIMUM mL IN A 30-DAY PERIOD
Kg	lbs	mL		
1	2.2	100	2.5	5
2	4.4	200	5	10
3	3.3	240	6	12
4	8.8	320	8	16
5	11	400	10	20

Figure 6 Maximum allowable blood draw volumes

11.2. Describe the process/system for assuring confidentiality and the privacy of the research participants/communities

The record form was unidentifiable enrolled patients; therefore, name or hospital number would not be filled in the record form. The data would be kept in secret files and only principal investigators and recorders could access to these data during recruitment of the participants, during data collection, during transcription, and data analysis, and dissemination of research results.

11.3. Benefits of the study for participants and the community/country including how findings of the study use for strengthening community.

The result of this study may be the choice of post-extubation via nSIPPV and nHFO (head to head comparison)

11.4. Informed consent process: Process/method of invitation the participants to participate in the research, such as personal contact, referral from other(s), brochure, and announcement, etc.

The parents of intubated neonates without exclusion criteria would be pursued to enrolled in this study by the dedicated nurse. The parents would receive informative documents with explaining the entire data about 30 to 60 minutes or until the parent were crystal clear about the study detail by the nurse. If the parents allowed the patients to enroll in the study, they would sign the signature in the informed consent's document.

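### Pre-extubation pCO2 is already collected, but no analysis in 10.14 uses it; the listed between-infant analyses would gain from it, while the primary within-infant test would not

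*Combined protocol and SAP*

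**What the plan says.** The baseline value is in hand. Section 10.10 states "The first blood gas before extubation was routine obtained". Section 11.1 counts that draw in the study's blood volume: "The volume of blood sample was 0.4 mL including before and after tests". Section 10.12 says "Participant's data and blood gas's result will be recorded in record form".

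Section 10.14 lists these analyses:

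- "Carry-over effect = Independent t-test comparing intraindividual sums of measurements from both periods"
- "Treatment effect = Independent t-test comparing intraindividual differences of measurements of nHFOV versus nSIPPV from both periods"
- a dependent t-test, and an entry for regression analysis with no further detail
- "Category (reintubation): logistic regression"
- "Time to event (reintubation): Cox's proportion model"

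No covariate is named for any of them, and pre-extubation pCO2 appears neither as a covariate nor as a change from baseline. Randomisation (10.10) is stratified by gestational age and oxygen index. That index is built from mean airway pressure, FiO2 and PaO2, so it has no CO2 term and stratification does not balance baseline pCO2.

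**The concern.** pCO2 is the primary outcome, and a high PaCO2 is part of one reintubation criterion in 10.10. Its pre-extubation value is therefore a natural prognostic covariate. Where infants are compared with other infants, leaving it out keeps variance in the error term that could be removed, and leaves any chance imbalance uncorrected.

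The analysis most affected is the carry-over test. Section 10.10 provides no washout between modes, so this test is the only check on carry-over that 10.14 lists. It compares infants between sequences and is weak at 12 per sequence. The reintubation models, which serve the secondary objective, are also between-infant comparisons.

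**Working it through.** **Inputs from 10.9.** Means 35.1 and 43 (difference 7.9); SDs 7.5 and 6; reintubation 10% v 17%; ratio 1:1.

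**The plan's own sizes.** (1.96 + 0.842)² × (7.5² + 6²) / 7.9² = 11.60, so 12 per group. The two-proportion formula gives 373 per group, or 401 with continuity correction. All three match 10.9 at two-sided alpha 0.05 and 80% power. The other alpha and beta values displayed there do not reproduce them.

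**Assumptions (not in the documents).** r is the correlation of baseline pCO2 with each later pCO2, and r12 the correlation between the two later values. The sum difference to be detected and the odds ratio per SD of baseline are also assumed.

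**1. Primary test on differences.** The share of variance explained by baseline is (r01 − r02)² / [2(1 − r12)], where r01 and r02 are its correlations with periods 1 and 2.

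- Equal correlations: 0.
- r01 = 0.6, r02 = 0.4, r12 = 0.5: 0.04 / 1 = 4%.
- Correlation decaying with time (r01 = r12 = ρ, r02 = ρ²): ρ²(1 − ρ)/2, at most 7.4%.

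With 12 per sequence, all correlations 0.5 and an assumed effect of 4, simulated power is 79% unadjusted and 76% adjusted. There is no gain to claim.

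**2. Carry-over test on sums, 12 per sequence.** The average variance is (56.25 + 36)/2 = 46.125. With r12 = 0.5, the SD of the sum is √(2 × 46.125 × 1.5) = 11.76 and the standard error is 11.76 × √(2/12) = 4.80. For a sum difference of 10 the noncentrality is 10/4.80 = 2.08, and power on 22 df is 51%.

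Adjusting for baseline gives R² = 2r²/(1 + r12). The standard error is multiplied by √[(1 − R²)(1 + 1/20)], and there are 21 df.

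| r | R² | Standard error | Power |
|---|---|---|---|
| unadjusted | – | 4.80 | 51% |
| 0.1 | 0.013 | 4.89 | 50% |
| 0.2 | 0.053 | 4.79 | 51% |
| 0.3 | 0.120 | 4.62 | 54% |
| 0.5 | 0.333 | 4.02 | 66% |

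Simulation at r = 0.5 gives 52% and 67%. If r and r12 are both 0.7, simulated power goes from 47% to 81%. For a sum difference of 7.9 instead of 10, with r12 = 0.5, the normal approximation gives 38% unadjusted, 42% at r = 0.3 and 52% at r = 0.5.

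**3. Reintubation, logistic model at 373 per arm.** Expected events are 373 × (0.10 + 0.17) = 101, so one more covariate is easily carried. In simulation (4,000 trials per scenario), power went from 79.9% to 80.6% at an odds ratio of 1.5 per SD of baseline pCO2, from 80.1% to 81.9% at 2.0, and from 81.0% to 86.0% at 3.0. The Cox model was not simulated.

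**The case against.** **The documents do not rule out adjustment.** Section 10.14 lists regression without covariates. It is silent, and the strata (gestational age and oxygen index) are at least as obvious candidates. That is fair. But a covariate chosen after the data are seen is open to challenge, which is a reason to name it beforehand.

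**The correlation may be low.** The baseline gas is taken on invasive ventilation, so it partly reflects ventilator settings, and the extubation criterion of PaCO2 below 60 narrows its range. This stands. At r of about 0.2 or less, adjustment at 12 per sequence gains nothing or costs a little power.

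**The gains belong to different trials.** Section 10.9 gives both 12 and 373 per group and does not say which is the enrolment target. At 12 per arm, about 3 reintubations are expected (24 infants at an average of 13.5%) and power for 10% v 17% is about 7%. No covariate rescues that, and the adjusted logistic fit could be unstable. At 373 per arm, the pCO2 comparisons are not short of power for a difference of 7.9. This stands, so the gains must not be combined.

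**Adjustment changes what is estimated.** Odds and hazard ratios become conditional on baseline pCO2. This is true and should be stated in the SAP.

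A reader might go further in two ways that the documents do not support:

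- *The plan forgoes a large gain in a first-period comparison.* At 12 per sequence, power for such a contrast would go from 78% to 79%, 86% and 96% at r = 0.3, 0.5 and 0.7. But 10.14 lists no such comparison, so these figures are not a loss in any planned analysis.
- *A mixed model with baseline would recover infants who have only one later gas.* Infants reintubated within the 4 hours are withdrawn under 10.7 and excluded under 10.10. A change of model alone does not bring them back.

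**Conclusion.** The point holds as a modest efficiency gain in the between-infant analyses that 10.14 lists. It is not an error in the stated sample sizes, which reproduce, and it does not touch the primary treatment-effect test.

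The larger gain is in the carry-over test, about 3 points of power at r = 0.3 and 15 at r = 0.5 under the assumptions above. Even so, the test stays weak. The sum difference of 10 used here is a difference in carry-over larger than the 7.9 treatment difference that the trial was sized on. For reintubation the gain is about 1 point at modest prognostic strength, and reaches about 5 only at an odds ratio near 3 per SD, which nothing in the documents supports or excludes. Every one of these sizes rests on assumed correlations or odds ratios.

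**What to change.** In 10.14:

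- Replace the t-test on sums with an analysis of covariance of the within-infant sum on sequence, with pre-extubation pCO2 (continuous) as covariate.
- Name pre-extubation pCO2 (continuous) as a prespecified covariate in the logistic and Cox reintubation models, and say that the resulting ratios are conditional on it.
- Leave the primary test on within-infant differences without it.
- If a first-period comparison between sequences is reported as a sensitivity analysis because there is no washout, adjust it the same way and state its supporting role.

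The cost is SAP wording and one degree of freedom per model, with a slight loss of power at 12 per sequence if r is about 0.2 or less. No new sample or data item is needed.

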11.5. Procedure specifying for research participant withdrawal from the study

If enrolled participant met the withdrawal criteria, the participant was withdrawal and not replaced. The subjects withdrawn were followed-up as routine care.

11.6. Clearly indicate person(s) responsible for payment for treatment of complications and adverse effects

None

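### Infants reintubated during the 4-hour crossover are excluded in one section and covered by intention-to-treat in another, and the plan does not say whether their events count in the 7-day analysis or the interim rates

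*Combined protocol and SAP*

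**What the plan says.** Four sections of the protocol deal with an infant reintubated in the first 4 hours.

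- Section 10.10: "The participant was excluded if severe respiratory failure with reintubation during 4 hours after intervention". Later in the same section: "In case of extubation failure, the study period was ended prematurely for the respective infant", with a pCO2 measured at that time.
- Section 10.7 lists "Reintubation during 4-hour cross-over study" as a withdrawal criterion.
- Section 11.5: for an infant meeting a withdrawal criterion, "the participant was withdrawal and not replaced", with follow-up as in routine care.
- Section 10.14: "Intention-to-treat analysis was applied in case of treatment failure".

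All of this comes after randomisation: "An envelope was drawn by a dedicated nurse immediately after enrolment of the infant".

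The secondary objective in section 7 is 7-day reintubation, nHFO against nSIPPV, "from the latter NIV mode in parallel study". It gives no time origin. Section 10.8 stops the study if reintubation exceeds 30% on nHFO or 60% on nSIPPV, or if the two differ by more than 30%. It defines neither numerator nor denominator. No analysis set is defined in section 10.14 or elsewhere in the text.

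**The concern.** The event that triggers exclusion is the event being counted. Removing randomised infants because they had the outcome takes events out of the numerator and infants out of the denominator, so the groups compared are no longer those randomised. Failures in hours 2 to 4 happen on the latter mode itself and would be lost from its rate. Failures in hours 0 to 2 happen on the other mode, and the secondary objective does not say where they belong, because these infants never received the latter mode.

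Two analysts following different sections could therefore report different 7-day results from the same data. The interim rates have the same gap, and there excluding early events can only lower the observed rate. The trial is unblinded, so a choice made after the data are seen would be hard to defend.

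**Working it through.** **1. The plan's own figure.** Inputs from section 10.9: 0.10 against 0.17, ratio 1. The calculator image shows two options each for alpha and beta; only 0.05 (two-sided) and 0.2 reproduce its results.

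n = [1.96·√(2 × 0.135 × 0.865) + 0.8416·√(0.10 × 0.90 + 0.17 × 0.83)]² / 0.07² = 372.9, so 373 per arm, or 401 with the continuity correction. Both figures reproduce. Section 10.9 does not say which is adopted, and neither allows for exclusions.

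**2. How many reintubations are early?** The documents give no figure. As an anchor, a constant hazard over 168 hours gives [1 − 0.90^(4/168)] / 0.10 = 2.5% of events in the first 4 hours (2.6% for a rate of 0.17). Early clustering is represented by an assumed 5% to 20%.

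**3. Power if early events are excluded.** Let f be the early share, equal in both arms. The analysed rate is q = p(1 − f)/(1 − fp), the analysed number is 373(1 − fp), and the events removed are 373·p·f. Power = Φ[(|q₂ − q₁| − 1.96·s₀)/s₁], where s₀ is the pooled and s₁ the unpooled standard error.

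| f | Analysed rates | Events removed (nHFO, nSIPPV) | Power at 373 |
|---|---|---|---|
| 0 | 10.0% vs 17.0% | 0, 0 | 80.0% |
| 2.5% | 9.8% vs 16.6% | 0.9, 1.6 | 79.1% |
| 5% | 9.5% vs 16.3% | 1.9, 3.2 | 78.2% |
| 10% | 9.1% vs 15.6% | 3.7, 6.3 | 76.3% |
| 20% | 8.2% vs 14.1% | 7.5, 12.7 | 71.8% |

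At 401 per arm, power falls from 82.8% to 81.1% at f = 5% and to 74.9% at f = 20%.

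**4. False positives if early failure differs by sequence.** Set the true 7-day rate to 17% in both arms and exclude a proportion e of infants: q = (0.17 − e)/(1 − e), n = 373(1 − e).

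- e = 2% in both: 5.0%.
- e = 3% against 2%: q = 0.14/0.97 = 14.4% against 0.15/0.98 = 15.3%, and the two-sided test rejects 6.3% of the time. When all reintubations are counted, simulation gives 5.0%.
- At the even-spread anchor with one arm doubled (0.85% against 0.43%): 5.2%.

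These cases assume equal 7-day totals, so later failures must offset the early difference.

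**5. Interim limits.** If a share f is excluded, the observed rate reaches a limit t only when the true rate is t/(1 − f + tf).

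- nHFO, 30% limit: 0.30/0.9825 = 30.5% at f = 2.5%; 0.30/0.965 = 31.1% at 5%; 0.30/0.86 = 34.9% at 20%.
- nSIPPV, 60% limit: 0.60/0.99 = 60.6%; 0.60/0.98 = 61.2%; 0.60/0.92 = 65.2%.

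**6. Primary pCO2.** With 12 per group (24 infants), the expected loss runs from 24 × 0.025 × 0.10 = 0.06 to 24 × 0.20 × 0.17 = 0.8 infants.

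**The case against.** The strongest reply is that the plan already keeps these infants in. Section 10.14 ties intention-to-treat specifically to treatment failure, and section 10.10 speaks of the study period ending early. Together these can be read as saying that the infant leaves the crossover procedures and stays in the analysis. That reading is plausible, and under it nothing is lost. But the sentence names neither the 4-hour reintubations, the 7-day outcome nor the interim rates, and it sits against a plain statement that the infant is excluded. It also cannot say which mode an hour 0 to 2 failure belongs to.

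A second reply is that the flow diagram in section 8 might show the handling. It is not reproduced in the text available for this review, so the point is limited to what the written sections say.

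A third is that the numbers are small. That stands at the anchor: one or two events per arm and less than one percentage point of power. Both sequences also meet both modes within the 4 hours, which would tend to narrow any difference in early failure between them.

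A fourth is that analysing by sequence from the first mode is a choice of estimand and not forced by the text; a clock starting with the latter mode is a natural reading of section 7. That is fair. However, infants who reach the latter mode have been selected by surviving 2 hours on the other one, so that analysis suits a supplementary role.

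**Conclusion.** The conflict is real and should be fixed. Followed as written, the exclusion removes outcome events after randomisation and lowers the observed reintubation rates; the intention-to-treat sentence may be intended to prevent this but does not say so. The size cannot be derived from the documents. It is slight if events are evenly spread (79.1% power against 80.0%) and moderate if 5% to 20% are early (78.2% to 71.8%). Bias needs unequal early failure: 3% against 2% gives 6.3% false positives.

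Three stronger conclusions are not supported. A reader might infer that the sponsor has settled on dropping these infants; the intention-to-treat sentence leaves that open. A reader might expect serious inflation of the error rate; early failure of 4% against 2% would give 10.3%, but needs 4/17 = 23.5% of one arm's reintubations in the first 4 hours, beyond the range assumed here. A reader might infer that the primary pCO2 result is compromised; fewer than 1 of 24 infants would be lost. The section 10.14 tests need both periods, so that result is a completers' analysis without the label.

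**What to change.** Leave the rule that ends crossover procedures at reintubation unchanged. Then:

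- Reconcile sections 10.7, 10.10, 11.5 and 10.14 to say that these infants leave the crossover procedures but stay in the analysis.
- Analyse 7-day reintubation (logistic and Cox) by randomised sequence, that is, by assigned latter mode, in all randomised infants who were extubated and started NIV. Count every reintubation from the start of the first NIV mode, including hours 0 to 4. Randomisation is not a suitable time origin, because the envelope is drawn at enrolment and section 11.4 recruits infants who are still intubated. Report any infant randomised but never extubated.
- Add a supplementary analysis of infants who reached the latter mode.
- For section 10.8, include early reintubations with the same randomised-sequence numerator and denominator, and list hour 0 to 4 events separately by mode in use. Do not use a denominator based on the last mode received: an infant would enter it for the first-period mode only by failing in hours 0 to 2, which is itself selection on outcome.
- Label the two-period pCO2 tests as a completers' analysis, report the number not included by sequence, and state whether the pCO2 taken at failure is used.

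The cost is wording only. The reintubation is already known when the infant is withdrawn, so no visit or sample is added. The one small downside is that hour 0 to 2 failures are counted under a mode not received, which is why the supplementary analysis is needed. The change should be made before any interim look or final analysis.
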